Chronic low-back pain exacerbation procedure: Co-investigators and/or trained study staff will conduct the cLBP exacerbating straight leg-raise test, which is commonly used to assess mobility and pain severity in those with low-back pain (Mens, Vleeming et al. 1999, Roussel, Nijs et al. 2007, Kwong, Virani et al. 2013, Bruno, Millar et al. 2014). This procedure significantly increases behavioral and neural pain responses for 10-15 minutes (Apkarian, Krauss et al. 2001, Sharma, Gupta et al. 2011, Wasan, Loggia et al. 2011, Loggia, Kim et al. 2013). Session 1 will determine if the straight leg raise test will reliably exacerbate cLBP and allow patients to decide if they are willing to perform subsequent straight leg raises. Co-investigators and/or trained staff will first instruct patients to lie in supine position for 15 seconds before collecting baseline pain ratings. For each patient, we will first measure the straight leg angle/height required to produce a 2-point VAS pain intensity increase using a goniometer [70]. With the aid of study staff, participants will again perform a straight leg-raise ranging from 15-60° (Rebain, Baxter et al. 2002, Summers, Malhan et al. 2005), depending on the angle/height required to produce the targeted pain increase and hold the position for 10 seconds. After lowering their legs, we will assess if the patient's pain ratings increased to the targeted pain increase compared to baseline pain ratings (Wasan, Loggia et al. 2011). This procedure will be repeated up to three times to ensure inter-maneuver reliability (Wasan, Loggia et al. 2011). Since this procedure can exacerbate pain for up to 15 minutes, we will wait at least 20 minutes between tests to confirm that pain returned to baseline. The leg-raise angle/height corresponding to a 2-point VAS pain increase will be targeted in each subsequent testing session. This session should take approximately 2.0 hours or less to complete.

Procedures

Pre Rest + Heat: A thermal probe will be placed on the back of the “unaffected” calf (i.e., non-responsive to SLR) while patients lie in the supine position. They will be instructed to “rest with your eyes closed” for 5 minutes. We will administer the so-called “Heat” series that includes 10 alternating, 12-second plateaus of noxious (49°C) and 35°C stimulation. VAS pain intensity, VAS unpleasantness, and numerical pain ratings will be collected after the series has completed. We will then remove the calf from the probe holder.

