research technician will issue study assessments to the subject. We will recalibrate each participant's leg raise height/angle required to elicit a 2-point pain increase employing the methods described in Session 1. An ACTRI nurse will then insert the IV catheter into the non-dominant arm of each participant. As previously employed (Zeidan, Adler-Neal et al. 2016) for safety purposes, blood pressure, respiration, oxygen saturation, and heart rate will be systematically monitored/recorded. These sessions should take approximately 1.0 hour to complete.

Pre Rest + Heat: A thermal probe will be placed on the back of the "unaffected" calf while patients lie in the supine position. They will be instructed to "rest with your eyes closed" (~ 5 minutes). We will administer a "Heat" series that includes 10 alternating, 12-second plateaus of noxious (49°C) and 35°C stimulation. After completion, we will collect pain ratings.

Pre Rest + SLR: The procedures employed in Pre Rest + SLR will be matched to those employed in Session 1. Briefly, patients will lie in the supine position and be instructed to "rest with your eyes closed". VAS pain ratings will then be collected. With the aid of a technician, participants will then lift their legs to the angle/height calibrated to produce a 2-point VAS pain increase. After completion, we will collect pain ratings.

Bolus: An ACTRI nurse will then initiate the naloxone/saline bolus (based on weight) for approximately 8 minutes.

Pre Meditation + SLR: After completion of the bolus (~8 minutes), a study technician will aid participants to lift their legs to the height/angle calibrated to produce a 2-point VAS pain increase. Participants in the mindfulness and non-mindfulness meditation groups will then be instructed to "begin meditating until the end of the session" (Zeidan, Martucci et al. 2011, Zeidan, Emerson et al. 2015). An ACTRI nurse will then initiate the naloxone or placebo-saline infusion. After completion, we will collect pain ratings.

Post Meditation + Heat: A thermal probe will be placed on the back of the "unaffected" calf while patients lie in the supine position and during meditation. We will administer a "Heat" series that includes 10 alternating, 12-second plateaus of noxious (49°C) and 35°C stimulation. After completion, we will collect pain ratings.

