Patients will return to the ACTRI to complete session 7 and will follow the same procedures (except for drug administration) as Session 6. Participants must wait 2 days to participate but no longer than 7 days to complete Session 7. Drug symptomology will be assessed after each session.

Primary Outcome Measure(s):

1. Visual Analog Scale (VAS) and numerical rating scales (NRS): Pain ratings (VAS pain intensity, VAS unpleasantness, and numerical pain ratings) will be assessed in response to the straight leg raise test.
2. exploratory outcomes include those corresponding to "heat induced pain ratings" (i.e. thermal stimulation), and lying supine. The minimum rating ("0") is designated as "no pain" whereas the maximum ("10") is labeled as "most intense imaginable" or "most unpleasant imaginable." Higher numbers correspond to higher pain.
 - a. We will collect naloxone and saline induced changes in pain intensity and pain unpleasantness ratings

Sample Size Determination: Our targeted sample size is 60 cLBP patients (30/group). To conduct group comparisons among the two primary outcomes (naloxone + saline induced changes in pain intensity + unpleasantness) and to ensure an overall type I error rate < 0.05, we used conservative Bonferroni corrections ($p = .025$) in all power calculations. Employing the pilot data corresponding to our previous work (Wells et al., 2020), we fit repeated measures ANOVA models that include indicator

variables for group (mindfulness vs. sham) and drug (naloxone vs. saline). The estimated square root of mean square errors is 0.23 (23%) and 0.30 (30%) for pain intensity and pain unpleasantness, respectively. Thirty subjects will provide 80% power to detect a pain rating difference of 22% between the naloxone and saline conditions in the non-mindfulness group with an estimated SD of 0.3 (30%). We expect no meaningful differences in pain reductions between naloxone and saline infusion during mindfulness meditation. Thus, we will have 80% power to detect a significant group X drug type interaction. Finally, 30 subjects/group will provide 80% power to detect a significant group difference of 19% for pain intensity and 24% for pain unpleasantness. Such effect sizes parallel those observed in our pilot data (Wells et al., 2020). Statistical power will be also greater when pre-regimen pain ratings are entered as covariates to reduce residual variance.

Questionnaires for Study Assessments:

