10. HUMAN SUBJECTS

Total number of subjects to be enrolled at UCSD

Our targeted sample size is 60 cLBP (30/group). We have exhibited a relatively low attrition rate on previous work, thus we request permission to enroll 74 participants with the goal of retaining 60 participants.

Age: Age will range between 18 and 65 years.

Sex: We will have equal males and females in each group. Groups will be matched by age and sex (15 males/15 females).

Ethnic background: We will include all ethnicities.

Health status: Participants must have a chronic low back pain diagnosis.

All study participants will be recruited from the ACTRI and the local community. We will employ our NIH-approved exclusion and inclusion criteria delineated in previous studies examining cLBP [27; 37; 42] as described below.

Eligibility Criteria: Patients will qualify for the study if medical evaluation demonstrates chronic low back pain that is evoked by lifting the legs. Existing medical records, per physician discretion and low back examinations will confirm diagnosis. Study physicians will confirm diagnosis (Fardon 2001, Wasan, Davar et al. 2005, Jamison, Ross et al. 2010, Wasan, Loggia et al. 2011, Fardon, Williams et al. 2014).

Inclusion criteria include those who:

- a) are between 18-65 years old;
- b) have ongoing chronic pain (pain intensity ≥ 3 on a 0-10 VAS);
- c) have radicular pain for at least 3 months;
- d) are not using other pain management procedures (i.e. CBD oil products) during the study period;
- e) are not taking opioids;
- f) if female and of a child bearing potential age, are not pregnant or nursing mothers;
- g) have not had back surgery within a year of the study start date;
- h) lack sensory/motor deficits that preclude participation in pain-inducing procedures;
- i) have no meditation experience;
- j) are straight leg raise test positive
- k) do not have any known allergies to naloxone or similar drugs

l) do not have a history of syncope and/or fear of needles/blood.

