14. POTENTIAL RISKS

This study may involve some risk, although the risks are considered low risk.

Straight Leg Raise Test

The straight leg raise test may produce the feeling of pain. The goal is to produce a targeted 30% increase (2-point increase) in the feeling of pain for no more than 20 minutes. Although rare (less than 2% occurrence), participants may feel discomfort and/or pain for up to 24 hours. The study team will ensure participants' comfort and/or safety during this procedure. Importantly, participants will have complete control of how much they raise their leg.

Reproductive Risks

Due to unknown risks and potential harm to the unborn fetus, sexually active women of childbearing potential must use a reliable method of birth control while participating in this study.

Pregnant women are excluded from participation in this study. Because some methods of birth control are not 100% reliable, a urine pregnancy test will be required at least 10 days from subjects' last normal menstrual period, if they are a sexually active woman of childbearing potential and not using reliable birth control.

Randomization

Participants will be instructed in the consent form with the following “You will be assigned to a study group at random (by chance). Your assignment is based on chance rather than a medical decision made by the researchers. The study group you are assigned to might not be the group you would prefer to be in. Your assigned study group might also prove to be less effective or have more side effects than the other study groups(s), or other treatments available for your condition. You will also be randomly administered either naloxone or saline (or vice versa) in experimental sessions 6 and 7 which may influence some of their responses.”

Psychological Assessments

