15. RISK MANAGEMENT PROCEDURES AND ADEQUACY OF RESOURCES

The study was carefully designed to minimize or negate any potential risk/discomfort to participants.

An Independent Monitoring Committee (IMC) will monitor the activities of this study for purposes of evaluating subject safety and study integrity. The key elements of the IMC plan include protection of participant privacy, database protection, adverse event reporting, data quality and safety reports, participant compliance, and safety review plans. For the proposed study, the IMC will review the progress of and safety after 20, 40, 60 and 74 (if needed) study participants have completed all study procedures. There will be no fee for the independent monitoring of the proposed studies. [name] will oversee all experimental procedures of the proposed research activities. In the event of an adverse safety event, protocol deviations and adverse events will be promptly (less than 24 hours) reported to the IMC and the IRB.

This study will be stopped prior to its completion if: (1) the intervention is associated with adverse effects that call into question the safety of the intervention; (2) difficulty in study recruitment or retention will significantly impact the ability to evaluate the study endpoints; (3) any new information becomes available during the trial that necessitates stopping the trial; or (4) other situations occur that might warrant stopping the trial.

We do not anticipate any events that would cause a cessation of the study. We have repeatedly demonstrated the ability to reliably recruit, retain, and execute data collection in a fashion that ensures successful completion of our experiments.

However, in the unforeseeable case that the proposed study has to be stopped, the PI will include an assessment of futility in the annual progress report to NIH. We will consult with the IMC and NCCIH to assess the impact of significant data loss due to problems associated with stopping the study.

Straight Leg-Raise Test: The straight leg-raise test is a commonly employed maneuver to examine chronic low-back pain severity and patient mobility. In the rare case that pain exacerbation is increased by greater than 4 VAS points and does not return to baseline levels after 40 minutes, we will discontinue patient study participation with reimbursement and a physician will evaluate the participant.

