- Any unanticipated problems, serious/unexpected adverse events, deviations or protocol changes will be promptly reported to the IRB and IMC.

Serious Adverse Event (SAE)

A serious adverse event (SAE) is one that meets one or more of the following criteria:

- Results in death
- Is life-threatening (places the subject at immediate risk of death from the event as it occurred)
- Results in inpatient hospitalization or prolongation of existing hospitalization
- Results in a persistent or significant disability or incapacity
- Results in a congenital anomaly or birth defect

An important medical event that may not result in death, be life threatening, or require hospitalization may be considered an SAE when, based upon appropriate medical judgment, the event may jeopardize the subject and may require medical or surgical intervention to prevent one of the outcomes listed in this definition.

Time Period and Frequency for Event Assessment and Follow-Up: Unanticipated problems will be recorded in the data collection system throughout the study. The PI will record all reportable events with start dates occurring any time after informed consent is obtained until 7 (for non-serious AEs) or 30 days (for SAEs) after the last day of study participation. At each study visit, the PI will inquire about the occurrence of AE/SAEs since the last visit. Events will be followed for outcome information until resolution or stabilization.

To assess relationship of an event to study intervention, the following guidelines are used:

1. Related (Possible, Probable, Definite)
 1. The event is known to occur with the study intervention.
 2. There is a temporal relationship between the intervention and event onset.
 3. The event abates when the intervention is discontinued.
 4. The event reappears upon a re-challenge with the intervention.
2. Not Related (Unlikely, Not Related)

There is no temporal relationship between the intervention and event onset. An alternate etiology has been established.

Expectedness of SAEs: The study PI and the IMC will be responsible for determining whether an SAE is expected or unexpected. An adverse event will be considered unexpected if the nature, severity, or frequency of the event is not consistent with the risk information previously described for the intervention.

Severity of Event: The following scale will be used to grade adverse events:

Mild: no intervention required; no impact on activities of daily living (ADL)

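### The leg-raise discontinuation rule cannot be met from a supine pre-raise rating of 6 or more on the 0-10 scale, although participants at 6 to 8 can be enrolled and tested

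*Protocol*

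**What the plan says.** The rule is in Protocol section 15, paragraph on the Straight Leg-Raise Test. A participant is withdrawn, with payment, and seen by a physician if "pain exacerbation is increased by greater than 4 VAS points and does not return to baseline levels after 40 minutes". The two conditions are joined by 'and'.

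Four other places fix how the rule works in practice:

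- **Scale.** Section 9, Primary Outcome Measure(s): zero stands for no pain, "whereas the maximum ('10') is labeled as 'most intense imaginable".
- **Entry.** Section 10, inclusion criterion (b): patients must "have ongoing chronic pain (pain intensity ≥ 3 on a 0-10 VAS". No upper limit is given.
- **Reference rating.** Section 9, Chronic low-back pain exacerbation procedure: staff "first instruct patients to lie in supine position for 15 seconds before collecting baseline pain ratings". The leg angle is then set to give a 2-point rise. Between calibration raises, "we will wait at least 20 minutes between tests to confirm that pain returned to baseline".
- **Repetition.** Section 9, Sessions 6 & 7: staff recalibrate the "leg raise height/angle required to elicit a 2-point pain increase employing the methods described in Session 1".

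Section 14 foresees pain that outlasts the raise. It is meant to last 20 minutes at most, but "Although rare (less than 2% occurrence), participants may feel discomfort and/or pain for up to 24 hours".

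**The concern.** A rule written as a rise on a bounded scale stops working once the starting point is close enough to the top. Here that happens well inside the range of people the trial may enrol. A participant who starts at 3, climbs to 7.5 and has not settled at 40 minutes must be withdrawn and evaluated. One who starts at 7, climbs to 10 and is still at 10 after 40 minutes does not meet the rule. The rule therefore leaves out some of the people in the most pain.

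It is also the only individual stopping rule for the leg raise that states a number. Where it cannot apply, nothing else in the plan sets a pain level or duration that obliges anyone to act. What is at stake is participant safety; estimation and testing are not involved.

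**Working it through.** The 4-point threshold is a chosen rule, not a derived figure, so there is no calculation of the plan's to reproduce. The check is arithmetic on a bounded scale.

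**Inputs**

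- Scale maximum: 10 (section 9, Primary Outcome Measure(s)).
- Starting rating *b*: the supine rating before the raise (section 9, exacerbation procedure). Section 15 does not define its baseline separately, so this is the natural reading.
- Rise required by the rule: more than 4 (section 15).
- Planned rise: 2 (section 9).

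**Formulas**

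- Largest possible rise = 10 − *b*.
- The rule can be met only if 10 − *b* > 4, that is *b* < 6.
- The planned rise can be reached only if 10 − *b* ≥ 2, that is *b* ≤ 8.

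| Start *b* | Largest rise, 10 − *b* | 2-point raise attainable? | Rise above 4 possible? |
|---|---|---|---|
| 3 | 7 | yes | yes |
| 4 | 6 | yes | yes |
| 5 | 5 | yes | yes |
| 5.9 | 4.1 | yes | yes |
| 6 | 4 | yes | **no** |
| 7 | 3 | yes | **no** |
| 8 | 2 | yes | **no** |
| 9 | 1 | no | no |
| 10 | 0 | no | no |

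The gap that matters is 6 to 8: the raise can be calibrated but the rule cannot be met.

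**Other readings of the rule**

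- If the 4 points are counted beyond the planned 2, the required rise is more than 2 + 4 = 6. Then 10 − *b* > 6 needs *b* < 4, and the rule is out of reach from 4 upward. The gap widens.
- If the reference is some other rating taken earlier, the same ceiling applies whenever that rating is 6 or more.

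**Number affected.** This cannot be calculated. The documents give no distribution of supine pre-raise ratings, and the entry rating of at least 3 describes ongoing pain, which need not equal the supine rating on the day.

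**The case against.** The strongest reply is that the section 15 rule says when discontinuation must happen, not that it happens only then. Staff remain free to stop anyone at 10 out of 10, and the general protections are substantial. Under section 14 the team undertakes to keep participants comfortable and safe during the raise, participants decide how far to lift the leg, and nurses or a physician oversee the naloxone procedures. Under section 15 experimental procedures are overseen, participants may withdraw without giving a reason, and any problematic medical occurrence counts as an adverse event, graded for severity and reported. "Events will be followed for outcome information until resolution or stabilization".

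Much of this stands. A reader might infer that a participant in persistent maximum pain would be left unattended. The documents do not support that inference; such a case would plausibly be handled as an adverse event. What survives is narrower: none of these protections names a pain level or duration that requires evaluation. The 20-minute wait in calibration comes closest, but it does not say what follows if pain has not settled.

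A second reply is that the rule has a coherent purpose. A rise above 4 is more than twice the planned 2, so it flags an excessive response, and it works for starts from 3 to just under 6. That is fair. It is a reason to keep the existing rule and add to it, rather than rewrite it.

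**Conclusion.** The point holds as a minor safety correction. The arithmetic is exact and needs no outside figure: from a pre-raise rating of 6 or more the rule cannot be met, and starts of 6 to 8 remain eligible and testable. It rests on reading baseline as the supine pre-raise rating; the alternative readings leave the gap as it is or widen it.

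Three larger conclusions might be inferred, and the documents support none of them.

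- *That the typical participant falls in the gap.* Section 14 equates the 2-point target with 30%. Taken relative to the starting rating, that implies 2 / 0.30 = 6.7. But section 14 does not say what the 30% is a percentage of, so it says nothing reliable about usual starting pain.
- *That the under-2% figure in section 14 sizes the problem.* It covers discomfort or pain lasting up to 24 hours at any level, not near-maximum pain, and the share starting at 6 to 8 would have to be invented. The number affected is unknown.
- *That the results are at risk.* The rule plays no part in the primary outcome or in the SAP's mixed-model ANOVA.

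**What to change.** Leave the mandatory discontinuation rule in section 15 as it is and add one sentence after it, for example:

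*In addition, if pain following a leg raise climbs to a rating at or near the top of the scale (threshold to be set by the study physicians) and has not settled to its pre-raise level 40 minutes later, a physician will assess the participant, whatever the size of the rise, and decide whether participation continues.*

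With a threshold of 9, for illustration, the sentence can apply from 6 (rise of 3), 7 (rise of 2) and 8 (rise of 1). The planned rise alone then meets the pain part for starts of 7 and 8 (7 + 2 = 9; 8 + 2 = 10), so persistence decides. With a threshold of 10 this is so only at 8. The physicians should choose with that in view. Persistence is a reasonable deciding factor, because 40 minutes is twice the intended maximum of 20.

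The added sentence should call for evaluation, not automatic withdrawal. A mandatory clause at 9 would remove someone who went from 8 to 9 and read 8.5 at 40 minutes, since return to baseline carries no tolerance.

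The cost is one amended paragraph, an occasional extra physician evaluation and, rarely, a discontinuation at the physician's discretion. If that follows Session 6, the second crossover session is lost, and with it that participant's naloxone-saline comparison.
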